# 3.2 Blinding

Because participants will elect whether they receive a booster vaccine or decline a booster vaccine, all participants will be aware of their group assignment. However, those participants in the booster group as well as study investigators will be blinded to study arm assignments within the booster group. A limited number of study staff handling and administering the vaccines will be aware of vaccine assignment and will be trained not to divulge vaccine assignment information to the investigator team. Study staff administering vaccine will not be involved with study surveillance to avoid involvement with measurement of study outcomes. The study will provide electronic documentation confirming that participants received one of the study vaccines (without indicating which vaccine) with date of vaccine administration (Appendix M: Documentation of Vaccine Administration). The electronic documentation of vaccine administration will be password protected to maintain blinding. At the completion of the trial, a designated group of investigators may be unblinded to the vaccine assignment groups to conduct analyses to address objectives related to vaccine efficacy.

# 3.3 Emergency Unblinding

Unblinding of vaccine assignment for a participant may be necessary due to a medical emergency or other significant medical event. Study participation will be discontinued for participants whose vaccine has been unblinded.

If unblinding is required:

- Only the Principal Investigator or delegated co-investigator or sub-investigator will make the decision to unblind the vaccine assignment.
- Only the affected participant will be unblinded.
- The study pharmacist(s)/designee at the study site will provide the unblinded vaccine assignment to the investigator.

The investigator will notify the sponsor designee as soon as possible after unblinding the participant.

# 4. SAMPLE SIZE AND POWER CONSIDERATIONS

# 4.1 Sample Size for Primary Objectives

Power and sample size are examined for both primary objectives to 1) compare VE between vaccinated arms (both NVX and mRNA) and the non-vaccinated comparison arm with a 2-sided alpha=0.05 superiority test and 2) determine non-inferiority of NVX 2023-2024 formula vaccine variant compared to a single dose of Pfizer mRNA 2023-2024 updated vaccine with a 1-sided alpha=0.05

confidence interval. The rate of CLI-associated SARS-CoV-2 infection, confirmed by COVID-19 rapid antigen test (RAT) in those not vaccinated with the 2023-2024 formulation is expected to be 80 per 100,000 person-days. We expect those choosing not to vaccinate in Fall 2023 to Spring 2024 to be a mix of unvaccinated and fully vaccinated but not boosted individuals, but to be conservative we will assume this group is solely comprised of fully vaccinated individuals. Using publicly available data on the historic case rates in Utah for COVID-19 from the week of October 2, 2022 to the week of May 21, 2023 [CITE https://coronavirus-dashboard.utah.gov/risk.html], the average rate of cases in those fully vaccinated in Fall 2022-Spring 2023 is 56.63 per 100,000 person-days for those fully vaccinated. From a survey conducted in spring of 2022, it has previously been reported that of those testing for COVID-19 44.2% report testing at a lab or clinic and 25.7% reported testing at a drive-thru clinic. Therefore, using at-home test kits to identify cases, we expect rates to be 43.1% higher (1/(0.257+0.442)) than what is shown on Utah's dashboard. This under-reporting adjustment to Utah's observed rates from last fall leads to a conservative estimate for the rate of CLI-associated SARS-CoV-2 infection, confirmed by COVID-19 rapid antigen test (RAT), in those not vaccinated with the 2023-2024 formulation to be 80 per 100,000 person-days. Using the same logic applied to the reports for those with a bivalent booster last fall, after adjusting for under-reporting, we estimate the infection rate to be 68 per 100,000 person-days in those vaccinated in Fall 2023 to Spring 2024.

For the superiority test of the first primary objective, on which the sample size is based, the null hypothesis that vaccine efficacy, or VE, of the 2023-2024 formula compared to no vaccination in Fall 2023-Spring 2024 is 0 is tested against the alternative that the VE is not equal to 0. That is,  $H_0$ : VE = 0 is tested against  $H_a$ : VE  $\neq 0$ . VE is calculated as 1- hazard ratio, HR, comparing those receiving the 2023-2024 formulation (either NVX or Pfizer) to those choosing not to be vaccinated in Fall 23 to Spring 24, times 100 or 100\*(1-HR). HR will be estimated using Cox proportional hazards models with  $\alpha$ =0.05. Table 1 provides the required sample size to yield 80% power to detect VE of 40%, 50%, and 60% or higher, assuming an attrition rate of 15% or less. We plan that the NVX and Pfizer arms will each have twice as many participants as the arm of those choosing no Fall 2023 to Spring 2024 vaccination, a ratio of 4:1. Calculations were made in PASS using the Multi-Arm Tests for Treatment and Control Survival Curves using Cox's Proportional Hazards Model. In 24 weeks of follow-up, the rate of 80 cases per 100,000 person-days equates to an event probability of 13.44%. This probability corresponds to a hazard rate of 0.14433. With a total of 1500 participants enrolled (1200 with 2023-2024 formulation and 300 without Fall 2023 to Spring 2024 vaccination), we have 80% power to detect a VE of 50% or more, even if we see 15% attrition. With 1500 enrolled and an observed VE of 50%, we anticipate there will be approximately 124 RAT confirmed symptomatic COVID-19 cases in total (41 in the not

vaccinated arm and 84 in the vaccinated arm) with no attrition, and 106 with 15% attrition.

Table 1. Relationship between Vaccine Efficacy and Sample Size, assuming a 4:1 ratio vaccinated with 2023-2024 formulation to not vaccinated in Fall 2023-Spring 2024 and 15% rate of attrition.

Lowest Detectable VE comparing between non-vaccinated	Sample size for 80% power			
and vaccinated (NVX and Pfizer combined) arms				
40%	2,378			
50%	1,460			
60%	960			

For the non-inferiority test in the second primary objective, the null hypothesis that the NVX vaccine of 2023-2024 formulation is inferior to the Pfizer vaccine of the 2023-2024 formulation is tested against the alternative that NVX is non-inferior. That is, H0:  $rVE < 0 + \delta$  is tested against Ha:  $rVE \ge 0 + \delta$ , where  $\delta$  is the "interval of equivalence", the range in which the effectiveness of the two vaccines would be considered clinically equivalent. Relative VE, or rVE, is calculated as 1- hazard ratio, HR, comparing those receiving the NVX 2023-2024 formulation to those receiving the Pfizer 2023-2024 formulation, times 100, or 100\*(1-HR). We believe an interval of -50% would be clinically acceptable. For example, if Pfizer reduces the hazard of infection by half, reducing the hazard by 25% (VE of 25%) would correspond to an rVE of -50%. Similarly if Pfizer shows 80% VE compared to the non-vaccinated, a NVX VE of 70% would correspond to an rVE of -50%. For the power calculations for the second primary objective, the significance level is  $\alpha$ =0.05.

Table 2 gives the power for testing the non-inferiority hypothesis with a sample of 600 enrolled patients per arm with an equivalence interval of -50%, with observed rVE ranging from -20 to 20 and observed rates of CLI-associated SARS-CoV-2 infection, confirmed by COVID-19 rapid antigen test (RAT) in the Pfizer arm ranging from 60 to 90 per 100,000 person-days. Additionally, an attrition rate of 15% from 600 is assumed. The power decreases as the observed case-rate in the Pfizer arm decreases or as the observed rVE decreases. Calculations were made in PASS 2023 using Non-Inferiority Tests for Vaccine Efficacy using the Hazard Ratio (Cox's Proportional Hazards Model). If we assume an infection rate of 60 per 100,000 person-days in the Pfizer vaccinated arm we have 81.12% power to determine non-inferiority of NVX for observed rVEs of 10 or greater.

Table 2. Power assuming 600 at enrollment for each group (NVX and Pfizer) accounting for 15% attrition for non-inferiority of NVX vs. Pfizer 2023-2024 formulations and a non-inferiority limit of -50 rVE.

Assumed rate of COVID- 19 infection in 100,000 person days for Pfizer	Possible Observed Relative VE							
2023-2024 formulation	20	10	5	0	-5	-10	-20	
arm								
50	86.88	74.60	67.13	59.16	51.02	43.03	28.63	
60	91.71	81.12	74.00	65.94	57.33	48.57	32.20	
70	94.84	86.12	79.58	71.75	62.97	53.70	35.66	
80	96.84	89.88	84.08	76.70	67.98	58.41	38.98	
90	98.08	92.68	87.66	80.86	72.41	62.72	42.16	

With a planned sample size of 600 per arm and 15% attrition, if the observed rate of infection in the Pfizer 2023-2024 updated vaccine formulation arm differs from 60 per 100,000 person-days, 600 participants in each arm assures 80% power to claim non-inferiority for observed rVE greater than 10, sometimes less than 10, as outlined in the table above. The grey cells in the table indicate which scenarios will have 80% power with 600 participants.

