6.1 Sample size & Power Considerations

6.1.1 Sample Size for Primary Objectives

Power and sample size are examined for both primary objectives to 1) compare VE between vaccinated arms (both NVX and mRNA) and the non-vaccinated comparison arm with a 2-sided alpha=0.05 superiority test and 2) determine non-inferiority of NVX 2023-2024 formula vaccine variant compared to a single dose of Pfizer mRNA 2023-2024 updated vaccine with a 1-sided alpha=0.05 confidence interval. The rate of CLI-associated SARS-CoV-2 infection, confirmed by COVID-19 rapid antigen test (RAT) in those not vaccinated with the 2023-2024 formulation is expected to be 60 per 100,000 person-days. We expect those choosing not to vaccinate in Fall 2023 to Spring 2024 to be a mix of unvaccinated and fully vaccinated but not boosted individuals, but to be conservative we will assume this group is solely comprised of fully vaccinated individuals. Using publicly available data on the historic case rates in Utah for COVID-19 from the week of November 20, 2022 to the week of July 30, 2023, 39 the average rate of cases in those fully vaccinated in Fall 2022-Spring 2023 is 39.64 per 100,000 person-days for those fully

vaccinated. From a survey conducted in spring of 2022, it has previously been reported that of those testing for COVID-19 44.2% report testing at a lab or clinic and 25.7% reported testing at a drive-thru clinic⁴⁰. Therefore, using at-home test kits to identify cases, we expect rates to be 43.1% higher (1/(0.257+0.442)) than what is shown on Utah's dashboard. This under-reporting adjustment to Utah's observed rates from last fall leads to a conservative estimate for the rate of CLI-associated SARS-CoV-2 infection, confirmed by COVID-19 rapid antigen test (RAT), in those not vaccinated with the 2023-2024 formulation to be 60 per 100,000 person-days. Using the same logic applied to the reports for those with a bivalent booster last fall, after adjusting for under-reporting, we estimate the infection rate to be 48 per 100,000 person-days in those vaccinated in Fall 2023 to Spring 2024.

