For the superiority test of the first primary objective, on which the sample size is based, the null hypothesis that vaccine efficacy, or VE, of the 2023-2024 formula compared to no vaccination in Fall 2023-Spring 2024 is 0 is tested against the alternative that the VE is not equal to 0. That is, H_0 : VE = 0 is tested against H_a: VE ≠ 0. VE is calculated as 1- hazard ratio, HR, comparing those receiving the 2023-2024 formulation (either NVX or Pfizer) to those choosing not to be vaccinated in Fall 23 to Spring 24, times 100 or 100*(1-HR). HR will be estimated using Cox proportional hazards models with α =0.05. Table 4 provides the required sample size to yield 80% power to detect VE of 40%, 50%, and 60% or higher, assuming an attrition rate of 15% or less. We plan that the NVX and Pfizer arms will each have twice as many participants as the arm of those choosing no Fall 2023 to Spring 2024 vaccination, a ratio of 4:1. Calculations were made in PASS using the Multi-Arm Tests for Treatment and Control Survival Curves using Cox's Proportional Hazards Model⁴¹. In 24 weeks of follow-up, the rate of 60 cases per 100,000 person-days equates to an event probability of 10.08%. This probability corresponds to a hazard rate of 0.10625. With a total of 1500 participants enrolled (1200 with 2023-2024 formulation and 300 without Fall 2023 to Spring 2024 vaccination), we have 80% power to detect a VE of 56.25% or more, even if we see 15% attrition. With 1500 enrolled and an observed VE of 50%, we anticipate there will be approximately 85 RAT confirmed symptomatic COVID-19 cases in total (30 in the not vaccinated arm and 55 in the vaccinated arm) with no attrition, and 72 with 15% attrition.

Table 4. Relationship between Vaccine Efficacy and Sample Size, assuming a 4:1 ratio vaccinated						
with 2023-2024 formulation to not vaccinated in Fall 2023-Spring 2024 and 15% rate of attrition.						
Lowest Detectable VE comparing between non-vaccinated and Sample size for 80% power						
vaccinated (NVX and Pfizer combined) arms						
40%	3,183					
50%	1,954					
56.25%	1,500					
60%	1,289					

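### Protocol 6.1.1 and SAP 4.1 size the same 1,500-participant comparison on different infection rates (60 and 80) and state different detectable VEs; the protocol's 85 cases labelled VE 50% are the VE 56.25% count

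*SAP*

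**What the plan says.** Both documents size the trial on the first primary objective, the superiority test of vaccinated (NVX and Pfizer combined) against non-vaccinated. Both describe 1,500 enrolled (1,200 and 300), 24 weeks of follow-up, 15% attrition and two-sided alpha of 0.05.

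- **SAP 4.1.** The infection rate "in those not vaccinated with the 2023-2024 formulation is expected to be 80 per 100,000 person-days". It is derived from a Utah dashboard average of 56.63 for October 2022 to May 2023. The event probability is 13.44% and the hazard 0.14433. The conclusion is "we have 80% power to detect a VE of 50% or more, even if we see 15% attrition", and Table 1 requires 1,460 for VE 50%.
- **Protocol 6.1.1.** The infection rate "in those not vaccinated with the 2023-2024 formulation is expected to be 60 per 100,000 person-days". It is derived from a dashboard average of 39.64 for November 2022 to July 2023. The event probability is 10.08% and the hazard 0.10625. The conclusion is "we have 80% power to detect a VE of 56.25% or more, even if we see 15% attrition", and Table 4 requires 1,954 for VE 50%.

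The expected rate in the vaccinated also differs: 68 in the SAP and 48 in the protocol.

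The protocol then gives an event count: "With 1500 enrolled and an observed VE of 50%, we anticipate there will be approximately 85 RAT confirmed symptomatic COVID-19 cases in total", split as "30 in the not vaccinated arm and 55 in the vaccinated arm) with no attrition, and 72 with 15% attrition".

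Protocol section 6 says that the analysis plans have been updated to revised power calculations with more accurate infection rates, and that surveillance was therefore lengthened from 20 to 24 weeks.

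**The concern.** One trial should have one planning rate, one detectable VE and one expected number of cases. Here a reader of the SAP is told that 1,500 participants suffice for VE 50%, while a reader of the protocol is told that VE 50% needs 454 more (1,954 − 1,500). These figures are what a reader uses to judge a null or imprecise primary result, so the conflict affects how the result is read even though it does not affect how it is computed.

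The protocol's case count is a separate problem inside a single document. With 80% power placed at VE 56.25%, a total of 85 cases at VE 50% looked too low for the stated rate.

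**Working it through.** **Inputs, from SAP 4.1 and protocol 6.1.1.** Rate 80 or 60 per 100,000 person-days; 168 days; N = 1,500 at 4:1; 15% attrition; two-sided alpha 0.05.

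**Formulas.**
- Non-vaccinated event probability: p0 = rate × 168 / 100,000
- Cumulative hazard: H = −ln(1 − p0)
- Vaccinated event probability: p1 = 1 − exp(−H × HR), with HR = 1 − VE
- Expected cases without attrition: 300 × p0 + 1,200 × p1; after attrition, D = 0.85 × that sum
- Required events (Schoenfeld): (1.96 + 0.842)² / (0.2 × 0.8 × ln(HR)²); required N = events / (0.2 p0 + 0.8 p1) / 0.85
- Power: Φ(√(0.16 D) × |ln HR| − 1.96)

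**Step 1: reproduce each document from its own rate.** Rate 80 gives p0 = 0.1344 and H = 0.14433; rate 60 gives p0 = 0.1008 and H = 0.10625. Both pairs match the printed values.

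| Rate | VE | N computed | N printed |
|---|---|---|---|
| 80 (SAP) | 40% | 2,372 | 2,378 |
| 80 (SAP) | 50% | 1,455 | 1,460 |
| 80 (SAP) | 60% | 958 | 960 |
| 60 (protocol) | 40% | 3,179 | 3,183 |
| 60 (protocol) | 50% | 1,952 | 1,954 |
| 60 (protocol) | 56.25% | 1,495 | 1,500 |
| 60 (protocol) | 60% | 1,286 | 1,289 |

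Every entry agrees within 6 participants, so neither table contains a formula error.

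**Step 2: locate the source of the difference.** Both documents divide the dashboard average by 0.257 + 0.442 = 0.699. This gives 56.63 / 0.699 = 81.0 (SAP, rounded to 80) and 39.64 / 0.699 = 56.7 (protocol, rounded to 60). The adjustment is the same; the dashboard window is not.

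**Step 3: power at N = 1,500 with 15% attrition.**
- Rate 80, VE 50%: D = 105.3; √(0.16 × 105.3) × 0.693 − 1.96 = 0.885; power 81.2%
- Rate 60, VE 50%: D = 78.5; √(0.16 × 78.5) × 0.693 − 1.96 = 0.496; power 69.0%
- Rate 60, VE 56.25%: D = 72.0; √(0.16 × 72.0) × 0.827 − 1.96 = 0.846; power 80.1%

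The Schoenfeld formula is pessimistic at 4:1 allocation. An unadjusted log-rank simulation (exponential times, 1,020 vs 255, two-sided 0.05, 20,000 runs per scenario) gives 79.2% power at rate 60 and VE 50%, and 88.9% at rate 80 and VE 50%.

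**Step 4: the protocol's expected cases at rate 60.**

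| | Non-vaccinated | Vaccinated | Total | After 15% attrition |
|---|---|---|---|---|
| Printed, labelled VE 50% | 30 | 55 | 85 | 72 |
| Computed, VE 56.25% | 30.24 | 54.50 | 84.7 | 72.0 |
| Computed, VE 50% | 30.24 | 62.09 | 92.3 | 78.5 |

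All four printed figures match VE 56.25%. Applying VE to the risk instead of the hazard gives 91 cases (77 after attrition) at VE 50%, so that reading does not rescue the label either.

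**The case against.** **The two documents may not be a matched pair.** The SAP is dated 11 October 2023 and names a protocol of the same date, while protocol 9.3 carries a June 2024 reporting cut-off. A later Appendix S1 may already use 60. This stands as a caution. It does not dispose of the conflict, because the supplied SAP already uses 24 weeks of follow-up and so is not simply the plan from before surveillance was extended. Nor does it touch the protocol's case count, where the error lies within one document.

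**The practical effect is small.** This stands. By simulation the SAP's claim is nearly met even at a rate of 60. Follow-up is a fixed 24 weeks and the expected case counts trigger nothing in either document.

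**Stronger readings that a reader might infer.**
- *The SAP's power statement is miscalculated, or the trial is underpowered.* Not supported: the statement is correct at the SAP's rate (81.2%), and the protocol openly states the larger detectable VE at its own rate.
- *The SAP's case count is also wrong.* It prints "approximately 124 RAT confirmed symptomatic COVID-19 cases in total (41 in the not" and "vaccinated arm and 84 in the vaccinated arm) with no attrition, and 106 with 15% attrition", and 41 + 84 is 125. But the exact values are 40.32, 83.55, 123.87 and 105.29; each printed figure is its exact value rounded up, and the total is given as approximate. This is a rounding artefact, not an error to pursue.
- *Nothing indicates which rate is current.* No sentence names it, but the text leans to 60. Protocol section 6 describes a revision to more accurate rates over the study period. The protocol's November-to-July window fits enrolment from November to February followed by 24 weeks; the SAP's October-to-May window does not.

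**Conclusion.** The point holds as a conflict between documents, together with one mislabelled event count in the protocol.

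- **Detectable VE.** For the same design, 80% power is placed at VE 50% (SAP) and at VE 56.25% (protocol). With 1,500 enrolled, moving from rate 80 to rate 60 lowers power at VE 50% from 81.2% to 69.0% by the formula that reproduces the printed tables, or from 88.9% to 79.2% by simulation.
- **Expected cases.** At rate 60 and VE 50% the protocol should show 92 (78 after attrition), not 85 (72), a shortfall of 7 cases before attrition and 6 after it.

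These results rest on the planning assumptions in the documents (proportional hazards, 4:1 allocation, 15% attrition applied as a loss of sample size) and, for the simulation, on an unadjusted comparison. That 60 is the current rate is an inference from the text. The matter is worth correcting, but of limited consequence.

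**What to change.** State one planning rate and one dashboard window in both documents, after confirming whether a later SAP already does so.

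If 60 is kept, update SAP 4.1 throughout:
- dashboard window as in protocol 6.1.1, with its average of 39.64
- vaccinated-arm rate 48
- event probability 10.08% and hazard 0.10625
- 80% power at VE 56.25%
- Table 1: 3,183 / 1,954 / 1,289 for VE 40 / 50 / 60%
- expected cases at VE 50%: 92 (78 after attrition)

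In protocol 6.1.1, either change the case count to 92 (30 + 62; 78 after attrition) or keep 85 (72) and label it VE 56.25%.

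The cost is a text correction. The SAP's stated detectable VE becomes less favourable (56.25% instead of 50%). Enrolment, endpoint, model, alpha and decision rule stay as they are.

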#### 5. DETERMINATION OF PROTOCOL DEVIATIONS

A list of protocol deviations include but are not limited to:

- Subject randomized and did not satisfy entry criteria
- Subject received the wrong treatment or incorrect dose
- Key study procedures missed or performed out of window

Number and percentage of subjects with a major protocol deviation by type of deviation and vaccine group will be reported.

#### 6. ANALYSIS POPULATIONS

#### **6.1 Modified Intent-to-Treat Population**

All participants who are randomized, received a study vaccine, and participated in study surveillance by responding to at least one surveillance contact during the SARS-CoV-2 circulation period (active surveillance) will be included in the modified intent-to-treat (mITT) population for the primary objectives. The mITT population will be the primary population for efficacy analyses and participants are analyzed according to their randomized treatment. For participants who were identified as not receiving a booster

(comparison group) they will be analyzed in that group under the mITT population, even if they subsequently do get a vaccine during the study period.

#### **6.2 Per Protocol Population**

The per protocol population will include participants who met eligibility criteria, received study vaccine per protocol, participated in study surveillance by responding to at least one surveillance contact during the SARS-CoV-2 circulation period (active surveillance), and did not receive another SARS-CoV-2 vaccine outside of the study during the study period. If participants were in the non-vaccinated comparison group but subsequently received a vaccination, they will be censored at that point.

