6.2 Statistical Analysis

The modified intent-to-treat (mITT) population will be the primary population for efficacy analyses and participants are analyzed according to their randomized treatment. All participants who are randomized, received a study vaccine, and participated in study surveillance by responding to at least one surveillance contact during the SARS-CoV-2 circulation period (active surveillance) will be included in the mITT population for the primary objectives. For participants who were identified as not receiving a 2023-2024 updated vaccine (comparison group) they will be analyzed in that group under the mITT population, even if they subsequently do get a 2023-2024 updated vaccine from elsewhere during the study period.

Additionally, a per protocol analysis will also be performed. The per protocol population will include participants who met eligibility criteria, received study vaccine per protocol, participated in study surveillance by responding to at least one surveillance contact during the SARS-CoV-2 circulation period (active surveillance), and did not receive another SARS-CoV-2 vaccine outside of the study during the study period. If participants were in the non-vaccinated comparison group but subsequently received a 2023-2024 updated vaccine, they will be censored at that point.

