# 7.2 Handling of Dropouts, Missing Data

The analyses will be done without adjustments for missing values. Subjects who withdraw or are lost to follow up will be censored at the last time of surveillance. Primary analysis will be analyzed on the mITT population and any missing swabs will be considered missing completely at random. A sensitivity analysis will repeat the primary efficacy analysis on the PP population.

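### The per-protocol set drops study vaccinees who take an outside dose but only censors decliners, which can bias per-protocol VE if outside dosing depends on infection

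*SAP*

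**What the plan says.** SAP 6.2 and Protocol 6.2 (Statistical Analysis) define the per-protocol population in nearly the same words. One condition of entry is that the participant "did not receive another SARS-CoV-2 vaccine outside of the study during the study period".

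The next sentence gives the comparison group its own rule. In the SAP: "If participants were in the non-vaccinated comparison group but subsequently received a vaccination, they will be censored at that point". In the Protocol: "If participants were in the non-vaccinated comparison group but subsequently received a 2023-2024 updated vaccine, they will be censored at that point".

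The primary population is mITT. There, SAP 6.1 keeps decliners in their group "even if they subsequently do get a vaccine during the study period", and study vaccinees are not removed for an outside dose. The per-protocol analysis has a supporting role: "A sensitivity analysis will repeat the primary efficacy analysis on the PP population" (SAP 7.2, listed again in SAP 8.3.3). Neither document explains why the two groups are handled differently.

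**The concern.** An outside dose is known only after follow-up has begun. For a decliner it ends follow-up, which is ordinary censoring. For a study vaccinee it decides whether the person was ever in the set, so follow-up before the dose is lost too. Membership of the vaccinated per-protocol group therefore depends on the future, and membership of the comparison group does not.

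This matters if infection influences later vaccination. Suppose infected people skip or postpone an outside dose. A vaccinee infected first then stays in the set with the event counted, while one who reaches the outside dose uninfected is removed with all of the event-free time. The vaccinated rate rises, the comparison rate does not, and per-protocol VE falls. A sensitivity analysis is useful only if its disagreement with the primary result means something, and this rule could create a disagreement by construction.

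**Working it through.** **1. The plan's own figure.** SAP 4.1, Table 1, gives 1,460 participants for VE 50%. Inputs from SAP 4.1: a comparison "with a 2-sided alpha=0.05 superiority test", 80% power, 4:1 allocation, event probability 13.44% (hazard 0.14433) over 24 weeks, and 15% attrition.

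- Events: (1.960 + 0.842)² / (0.2 × 0.8 × (ln 0.5)²) = 7.849 / 0.07687 = 102.1
- Mean event probability: 0.2 × 0.1344 + 0.8 × (1 − exp(−0.14433 × 0.5)) = 0.0826
- Participants: 102.1 / 0.0826, about 1,237; divided by 0.85, about 1,456

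This agrees with 1,460. The per-protocol rule does not enter the sizing.

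**2. The rule as written.** Let f be the share of study vaccinees who would take an outside dose, λ their infection rate, T the follow-up time and N their number. Assumptions, none of them in the documents: dose dates are uniform over follow-up, and anyone infected before the planned date does not take the dose (full deferral). Events are rare enough to ignore second-order terms.

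- Retained events: (1 − f)NλT from those with no planned dose, plus fNλT/2 from those infected before the planned date
- Retained person-time: about (1 − f)NT
- Observed rate: λ × (1 − f/2) / (1 − f)

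With censoring at the dose, person-time becomes (1 − f)NT + fNT/2. The ratio returns to λ, and VE is unbiased.

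**3. Numbers.** Observed VE = 1 − (1 − VE) × (1 − f/2)/(1 − f).

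| f (assumed) | Rate inflation | True VE 50% reads | True VE 20% reads |
|---|---|---|---|
| 2% | 0.99/0.98 = 1.010 | 49.5% | 19.2% |
| 5% | 0.975/0.95 = 1.026 | 48.7% | 17.9% |
| 10% | 0.95/0.90 = 1.056 | 47.2% | 15.6% |

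With half deferral, a true VE of 50% reads 49.3% at f = 5% and 48.6% at 10%. With no deferral it reads 50.0% at every f. Calculating without the rare-event shortcut, at 60 (Protocol) and at 80 (SAP) per 100,000 person-days, gives the same figures to within 0.1 point.

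**4. Simulation.** Single Cox runs used 60,000 per group, 80 per 100,000 person-days, true VE 50%, and 10% of decliners vaccinated elsewhere. With full deferral, the rule as written against censoring both groups gave 48.6% v 49.9% (f = 5%), 45.1% v 48.0% (10%) and 41.6% v 48.1% (20%). Each estimate carries Monte Carlo error of about 1 point, so the gaps are the informative part: 1.3, 2.9 and 6.5 points. With no deferral the two rules agreed within 0.3 points.

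**5. Sampling error.** With the SAP's 106 events after attrition, the SE of log HR is about 1/√(106 × 0.2 × 0.8) = 0.24. A VE of 50% then has a 95% interval of 1 − 0.5 × exp(±1.96 × 0.243), roughly 20% to 69%. At f = 5% the log HR moves by ln 1.026 = 0.026, about a tenth of an SE. At f = 10% it moves by ln 1.056 = 0.054, about a fifth. The Protocol's lower assumed rate gives fewer events and a larger SE.

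**6. rVE.** The inflation factor depends on f and not on λ. If outside uptake and deferral are the same in the two blinded randomized arms, it cancels from the NVX-to-mRNA hazard ratio to first order.

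**The case against.** Excluding randomized participants who take a non-study vaccine is a familiar per-protocol definition, and decliners were never assigned a vaccine. Study vaccinees have just had the season's updated dose, so few may seek another. The primary result, the sample size and the rVE decision rule all rest on mITT. All of this stands, and it is why the point is minor. It does not justify handling the same event in two ways within one VE comparison.

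Three stronger readings are tempting but not supported:

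- A reader might infer that the rule necessarily biases per-protocol VE. It does so only if outside dosing depends on infection. The Protocol's 90-day exclusion after infection (5.3) makes deferral plausible, but it governs eligibility for the trial vaccine and says nothing of outside doses during follow-up.
- A reader might treat every excluded vaccinee as event-free for the whole of follow-up, giving 1 − (1 − VE)/(1 − f). For a true VE of 50% that reads 49.0% at f = 2% and 44.4% at 10%; for 20% it reads 18.4% and 11.1%. Deferral implies freedom from infection only before the dose. Exclusion also removes events after it, so this formula doubles the excess that the mechanism supports.
- A reader might think both primary objectives are undermined. The primary VE analysis has no such exclusion, and rVE is largely protected by equal treatment of the two arms.

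**Conclusion.** The asymmetry is explicit in both documents, and nothing elsewhere repairs it. It can lower per-protocol VE, by about 0.5 to 3 points at a true VE of 50% (49.5% to 47.2%) and about 1 to 4 points at a true VE of 20% (19.2% to 15.6%). Those ranges assume 2% to 10% outside uptake among vaccinees, uniform dose dates and full deferral after infection. The bias is zero if outside dosing is independent of infection, and the documents support no particular value for uptake or deferral. The shift is small beside sampling error. It is confined to one sensitivity analysis of VE. The change is worth making because it is nearly free, and because agreement or disagreement with mITT is then easier to interpret.

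**What to change.** In Protocol 6.2 and SAP 6.2, delete the outside-vaccine condition from the per-protocol definition. Replace it with one rule: every participant, vaccinated or not, is censored at the date of any outside SARS-CoV-2 vaccine. Use the same wording in both documents, since for decliners the SAP now refers to any vaccination and the Protocol to the 2023-2024 updated vaccine.

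State the remaining entry criteria separately for vaccinees and decliners. Read literally, a decliner cannot satisfy the requirement of having been given the study vaccine as planned.

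The cost is a sentence or two. No new kind of data is needed: censoring decliners already requires dose dates, and the surveys and registry abstraction in Protocol 5.5.3.1, 5.5.3.2 and 5.5.4 capture outside doses for all participants. Those who opt out of registry access would rely on self-report or uploaded records. The change retains follow-up that the present rule discards.
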